7.1.3 Part 2 (MAD)

Part 2 is the MAD part of the study. After assessing eligibility during the 4-week screening period, approximately 16 participants (with a minimum of 2 of each gender per dose level cohort) will be enrolled in 2 sequential cohorts. Eligible participants in each cohort will come to the clinical unit on the day before the first study drug administration (Day -1), for baseline assessments and to confirm eligibility and will stay in the clinical unit for 14 days (13 nights), from Day -1 until Day 13. Participants will return to the clinical unit for outpatient PK blood sample collections on Day 15 (72 hours post-last dose), and Day 16 (96 hours post-last dose) as well as an outpatient follow-up visit that will take place 7 days after receiving the last dose of study drug, on Day 19 (between Day 19 and Day 22).

Each cohort will include 8 participants, 6 participants will receive ATH-399A and 2 participants will receive placebo. Dose levels of ATH-399A will be based on data from Part 1 (Part 1a and 1b) and recommendation from the SRC. Additionally, [REDACTED]

[REDACTED]

[REDACTED]

[REDACTED]

From Day 1 to Day 12, participants will receive either ATH-399A or placebo once daily (QD) for a total of twelve (12) consecutive days. On Days 1 and 12, participants will fast for a minimum of 10 hours prior to dosing and 4 hours following dosing. From Days 2 to 11, participants will fast for a minimum of 2 hours prior to dosing and 2 hours following dosing.

Following completion of each dose level (both cohorts), an SRC will review the safety and tolerability data through the follow-up visit of a minimum of 6 evaluable participants. The SRC will also review PK data for up to 24 hours post-last dose in at least 6 evaluable participants in

order to make decisions whether to escalate to the next planned dose level, decrease the next dose level, repeat a dose level, or to not evaluate any additional dose. The time interval when escalating the dose from the first dosing of Cohort 1 of the MAD to the first dosing of Cohort 2 of the MAD will be approximately 3.5 weeks.

Blood samples for PK will be collected pre-dose and at specified time points up to 96 hours post-Day 12 dose. Vital signs, ECG, telemetry, safety lab (including drug screen, cotinine, and alcohol breath test), C-SSRS, and physical and neurologic examinations will be performed at specified times. AEs will be recorded throughout the study. For details regarding the timing of specific procedures see [Table 3](#).

Additional Cohort: Following assessment of MAD dosing in participants, an additional cohort of approximately 8 participants will be evaluated at a dose level determined to be safe by the SRC. After assessing eligibility during the 4-week screening period, 8 participants (approximately equal numbers of males and females, with a minimum of 2 of each gender), aged >55-80 years, inclusive, will be enrolled. The study drug will be administered once daily (QD) in the fasted state for a total of twelve (12) consecutive days. On Days 1 and 12, participants will fast for a minimum of 10 hours prior to dosing and 4 hours following dosing. From Days 2 to 11, participants will fast for a minimum of 2 hours prior to dosing and 2 hours following dosing. Six participants will receive ATH-399A and 2 participants will receive placebo once daily (QD).

Eligible participants in this additional cohort will come to the clinical unit on the day before the first study drug administration (Day -1), for baseline assessments and to confirm eligibility and will stay in the clinical unit for 14 days (13 nights), from Day -1 until Day 13.

Blood samples for PK will be collected pre-dose and at specified time points up to 96 hours post-Day 12 dose. Vital signs, ECG, telemetry, safety lab (including drug screen, cotinine, and alcohol breath test), C-SSRS, and physical and neurologic examinations will be performed at specified times. Adverse events will be recorded throughout the study. Participants will return to the clinical unit for outpatient PK blood sample collections on Day 15 (72 hours post-last dose), and Day 16 (96 hours post-last dose) as well as an outpatient follow-up visit that will take place 7 days after receiving the last dose of study drug, on Day 19 (between Day 19 and Day 22). For details regarding the timing of specific procedures see [Table 3](#).

7.2 Justification for Dose

[REDACTED]

study progresses. The SRC recommendations should be based on results from a minimum of 6 evaluable participants in each dosing cohort.

Safety/tolerability data through the final follow-up visit for each of the 6 evaluable participants in a cohort along with PK data up to at least 48 hours post-dose in Part 1a and 1b (or 24 hours post-last dose in Part 2) will be assessed by the SRC prior to:

- a. Ascending from one dose-level cohort to the next higher dose level cohort in Parts 1a and 2,
- b. Prior to transitioning from Part 1a to Parts 1b and 2.

The SRC will stop dose escalation or descend to a dose level lower than the planned next higher dose level if any of the following criteria are met:

- One participant per cohort who receives ATH-399A experiences a serious adverse event (SAE) which is considered to be related to the study medication.
- Two participants per cohort who receive ATH-399A have QTc prolongation, defined as an average absolute (regardless of baseline value) QTcF >500 msec or an increase of QTcF > 60 msec above baseline, confirmed by repeating after 5 minutes, and determined post-dose.
- Two participants per cohort who receive ATH-399A exhibit hypotension, defined as resting supine diastolic blood pressure <40 mmHg persisting for at least 10 minutes on repeated assessment, or an asymptomatic or symptomatic fall in systolic blood pressure to below 80 mmHg, persisting for at least 10 minutes on repeated assessment.
- Two participants per cohort who receive ATH-399A exhibit hypertension, defined as an increase in resting systolic blood pressure to above 180 mmHg, persisting for at least 10 minutes, or an increase in resting diastolic blood pressure to above 105 mmHg, persisting for at least 10 minutes.
- Two participants per cohort who receive ATH-399A exhibit tachycardia, defined as resting supine heart rate >130 beats per minute, persisting for at least 10 minutes.
- Two participants per cohort who receive ATH-399A exhibit symptomatic bradycardia, defined as heart rate <40 beats per minute, or asymptomatic bradycardia, defined as resting supine heart rate <30 beats per minute while awake, persisting for at least 10 minutes, or clinically significant arrhythmia.
- One participant per cohort who receives ATH-399A exhibits abnormal liver tests defined as:
 - Aspartate aminotransferase (AST) or alanine aminotransferase (ALT) $>5X$ upper limit of normal (ULN).
 - AST or ALT $>3X$ ULN along with one of the following criteria:
 - sustained for more than 2 weeks or
 - total bilirubin level $>2X$ ULN or
 - international normalized ratio (INR) time $>1.5X$ ULN or
 - the appearance of fatigue, nausea, vomiting, right upper abdominal pain or tenderness, fever, rash, and/or eosinophilia ($>5\%$).
 - Alkaline phosphatase (ALP) $>3X$ ULN.
 - ALP $>2.5X$ ULN and total bilirubin $>2X$ ULN.

- ALP >2.5X ULN with the appearance of fatigue, nausea, vomiting, right upper abdominal pain or tenderness, fever, rash, and/or eosinophilia (>5%).
- One participant per cohort who reaches a plasma AUC₀₋₂₄ of $\geq 1,800 \text{ h}^*\text{ng/mL}$.
- Two participants per cohort who receive ATH-399A exhibit renal toxicity, defined as serum creatinine $\geq 1.5X \text{ ULN}$ (confirmed by repeating within 24 hours).
- Two participants per cohort who receive ATH-399A exhibit hematologic toxicity, defined as one or more of the following (confirmed by repeating within 24 hours):
 - Leukocyte count $<2.5 \times 10^9/\text{L}$
 - Neutrophils $< 1.3 \times 10^9/\text{L}$ and $< 1.0 \times 10^9/\text{L}$ for Afro-American participants
 - Platelet count $<75 \times 10^9/\text{L}$

In addition, the SRC may stop dose escalation or descend to a dose level lower than the planned next higher dose level at any time if the SRC determines that dose escalation would pose undue risk to participants. If dose escalation is not stopped, the SRC may recommend ascending to the planned next higher dose level cohort, ascending to a dose level lower than the planned next higher dose level, or may repeat dosing at the current dose level.

Initially, for Parts 1a and 2, the safety and any available PK data will be reviewed by the SRC in a blinded manner (e.g., without participant identifiers or using reblinded participant numbers), but if the SRC considers it necessary due to a safety concern, individual participant data or an entire cohort's data may be unblinded to the SRC to enable decision-making. Before any such unblinding, the reason for unblinding should be documented.

Unblinding to validate treatment group where stopping criteria is met will be determined by SRC members. Subsequent dose escalation or descent will depend on if stopping criteria was met by participants who received ATH-399A as opposed to placebo.

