- Two participants per cohort who receive ATH-399A exhibit tachycardia, defined as resting supine heart rate >130 beats per minute, persisting for at least 10 minutes.
- Two participants per cohort who receive ATH-399A exhibit symptomatic bradycardia, defined as heart rate <40 beats per minute, or asymptomatic bradycardia, defined as resting supine heart rate <30 beats per minute while awake, persisting for at least 10 minutes, or clinically significant arrhythmia.
- One participant per cohort who receives ATH-399A exhibits abnormal liver tests defined as:
 - Aspartate aminotransferase (AST) or alanine aminotransferase (ALT) >5X upper limit of normal (ULN).
 - AST or ALT >3X ULN along with one of the following criteria:
 - sustained for more than 2 weeks or
 - total bilirubin level >2X ULN or
 - international normalized ratio (INR) time >1.5X ULN or
 - the appearance of fatigue, nausea, vomiting, right upper abdominal pain or tenderness, fever, rash, and/or eosinophilia (>5%).
 - Alkaline phosphatase (ALP) >3X ULN.
 - ALP >2.5X ULN and total bilirubin >2X ULN.

- ALP $>2.5 \times$ ULN with the appearance of fatigue, nausea, vomiting, right upper abdominal pain or tenderness, fever, rash, and/or eosinophilia ($>5\%$).
- One participant per cohort who reaches a plasma AUC₀₋₂₄ of $\geq 1,800 \text{ h}^* \text{ng/mL}$.
- Two participants per cohort who receive ATH-399A exhibit renal toxicity, defined as serum creatinine $\geq 1.5 \times$ ULN (confirmed by repeating within 24 hours).
- Two participants per cohort who receive ATH-399A exhibit hematologic toxicity, defined as one or more of the following (confirmed by repeating within 24 hours):
 - Leukocyte count $<2.5 \times 10^9/\text{L}$
 - Neutrophils $< 1.3 \times 10^9/\text{L}$ and $< 1.0 \times 10^9/\text{L}$ for Afro-American participants
 - Platelet count $<75 \times 10^9/\text{L}$

In addition, the SRC may stop dose escalation or descend to a dose level lower than the planned next higher dose level at any time if the SRC determines that dose escalation would pose undue risk to participants. If dose escalation is not stopped, the SRC may recommend ascending to the planned next higher dose level cohort, ascending to a dose level lower than the planned next higher dose level, or may repeat dosing at the current dose level.

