Initially, for Parts 1a and 2, the safety and any available PK data will be reviewed by the SRC in a blinded manner (e.g., without participant identifiers or using reblinded participant numbers), but if the SRC considers it necessary due to a safety concern, individual participant data or an entire cohort's data may be unblinded to the SRC to enable decision-making. Before any such unblinding, the reason for unblinding should be documented.

Number of participants (planned):

It is planned to enroll approximately 76 healthy adult males and females for participation in this study:

Part 1a: approximately 40 healthy male and female participants, aged between 18-55 (inclusive) years.

Part 1b: approximately 12 healthy male and female participants, aged between 18-55 (inclusive) years with a minimum of 3 participants of each gender.

Part 2: approximately 16 healthy male and female participants, aged between 18-55 (inclusive) years with a minimum of 2 participants of each gender per cohort. And additional cohort of approximately 8 healthy male and female participants, aged between $>55-80$ (inclusive) years with a minimum of 2 participants of each gender.

Criteria for Inclusion:

1. Healthy, as determined by the Investigator based on a medical evaluation including medical history, physical examination, neurological examination, laboratory tests and cardiac monitoring. A participant with a clinical abnormality or laboratory parameters outside the reference range for the population being studied may be included only if, in the opinion of the Investigator, the finding is:
 - a) not clinically significant according to the Investigator judgement
 - b) unlikely to introduce additional risk to the participant,
 - c) will not interfere with study procedures or confound study results, and
 - d) is not otherwise exclusionary.
2. Population (Section 13.4):
 - a) Part 1a and 1b: Men and women, age 18-55 years inclusive at date of screening.
 - b) Part 2: Men and women aged 18-55 years inclusive at date of screening. Additional cohort: Participants of the additional cohort will be of approximately equal numbers of males and females, with a minimum of 2 of each gender, aged $>55-80$ years, inclusive.

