7.1.1 Part 1a (SAD)

After assessing eligibility during a 4-week screening period, approximately 40 healthy participants will participate in Part 1a. Each eligible participant will be assigned to 1 of 5 cohorts (8 participants per cohort) to evaluate a total of up to 5 single ascending dose levels. Proposed dose levels are:

Cohort 1: 5 mg

Cohort 2: 10 mg

Cohort 3: 20 mg

Cohort 4: 40 mg

Cohort 5: 80 mg

The starting dose will be 5 mg. Following completion of each ascending dose level, an SRC will review the safety and tolerability data through the follow-up visit of a minimum of 6 evaluable participants. The SRC will also review PK data for up to 48 hours post-dose in at least 6 evaluable participants in order to make decisions whether to escalate to the next planned dose level, decrease the next dose level, repeat a dose level, or to not evaluate any additional dose. The determination of the highest dose level for this study will be based on emerging safety/tolerability and PK data, as recommended by the SRC, but will not exceed the maximum dose currently outlined in the protocol.

For each dose level, 6 participants will receive ATH-399A and 2 participants will receive placebo. Each cohort will utilize sentinel dosing, with one participant receiving ATH-399A and one participant receiving placebo. Provided no clinically significant safety issues are noted in the 48 hours after dosing the initial 2 participants in the cohort, the 6 remaining participants in the cohort will be dosed. Before dosing the rest of the cohort, the Investigator will initiate a discussion via e-mail with the Sponsor's Medical Monitor (MM) or representative to review the available safety and tolerability data of the sentinel participants in order to make a decision regarding continuation of the study with the remaining 6 non-sentinel participants. In the case of

clinically significant safety issues or a sentinel stopping rule is present, then an ad hoc SRC meeting and/or a MM call can be necessary.

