9 STUDY TREATMENTS AND CONCOMITANT THERAPY

9.1 Study Treatments Administered

Study treatments to be administered in this study are provided in [Table 5](#).

Table 5: Study Treatments Administered

Treatment Name	ATH-399A	Placebo
Type	Drug	Drug
Dose Formulation	Capsule	Capsule with inert filler (Avicel)
Unit Dose Strength(s)	5 and 20 mg	N/A
Dosage Level(s)	5 mg to not more than 80 mg	N/A
Route of Administration	Oral	Oral
Use	Experimental	Placebo
IMP or NIMP	IMP	NIMP
Sourcing	Provided by the Sponsor	Provided by the Sponsor
Packaging and Labeling	Study treatment will be provided in HDPE bottles with child-resistant caps. Each bottle will be labeled as required per country requirement.	Study treatment will be provided in HDPE bottles with child-resistant caps. Each bottle will be labeled as required per country requirement.

IMP=Investigational Medicinal Product; N/A=not applicable; NIMP=Non-Investigational Medicinal Product;
TBD=to be determined

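### After a stopping criterion is met, the required SRC action is measured against the planned next dose, so its literal wording does not bar a smaller step up

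*Protocol*

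**What the plan says.** The required action appears in the same words in the Synopsis and in Protocol 7.3 (whose heading is lost to redaction in the public copy): "The SRC will stop dose escalation or descend to a dose level lower than the planned next higher dose level if any of the following" listed criteria is met. The list covers a related serious adverse event, QTc, blood pressure, heart rate, liver, renal and haematology limits, and an exposure limit that begins "One participant per cohort who reaches a plasma" AUC0-24 of 1,800 h*ng/mL or more.

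If escalation is not stopped, the same section lets the SRC go to the planned next level or choose "ascending to a dose level lower than the planned next higher dose level, or may repeat dosing at the current dose level".

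7.3 closes with: "Subsequent dose escalation or descent will depend on if stopping criteria was met by participants who received ATH-399A as opposed to placebo". The Synopsis account of the SRC lacks this sentence. It ends at "Before any such unblinding, the reason for unblinding should be documented".

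For routine cohort reviews in Part 1a, section 7.1.1 offers the options to "decrease the next dose level, repeat a dose level, or to not evaluate any additional dose" and sets an overall ceiling: the highest dose follows emerging data "but will not exceed the maximum dose currently outlined in the protocol". Table 5 gives the range as "5 mg to not more than 80 mg".

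**The concern.** A stopping rule should fix the next permissible dose by reference to the dose that caused the problem. Here the only dose named in the second branch is the planned next one. Every level between the dose that met the criterion and the planned next dose lies below that ceiling, so a reduced step up satisfies the letter of the branch.

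The two branches are joined by an or, so taking the second can be read as not stopping escalation. The same object phrase is then used in 7.3 with an upward verb, which shows that it can describe doses above the current one.

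At stake is whether SRC members would agree on the permitted doses just after a related serious adverse event, a liver signal or an exposure breach. In a first-in-human trial they should not have to interpret that rule. The exposure limit is the clearest case, because if exposure rises with dose, any step up makes a second breach more likely.

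**Working it through.** The plan states no figure to reproduce. The check compares the texts, counts the doses affected, and adds an illustration for the exposure limit.

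**1. The texts side by side**

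| Place | Situation | Direction | Reference dose |
|---|---|---|---|
| Synopsis and 7.3, required action | criterion met | down | planned next dose |
| Synopsis and 7.3, later paragraph | escalation not stopped | up | planned next dose |
| 7.3, closing sentence | after unblinding | up or down, by treatment received | none given |
| 7.1.1 | routine review | down | the next dose level |
| 13.1.5.1, more conservative options | general menu | down | planned next dose; a true descent is listed separately |
| 13.1.5.1, suspend option | after suspension | escalation resumes if no stopping rule is met | none given |

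No visible sentence caps the next cohort at the level that met a criterion. Section 10.1 covers sentinels within a cohort and life-threatening or fatal events, not the dose of the next cohort.

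**2. Doses admitted by the literal wording in Part 1a**

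Inputs: planned doses 5, 10, 20, 40 and 80 mg (7.1.1); capsules of 5 and 20 mg (Table 5), hence 5 mg steps. Doses strictly between the triggering dose and the planned next dose:

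| Criterion met at | Planned next | Admitted step up | Largest ratio |
|---|---|---|---|
| 5 mg | 10 mg | none | – |
| 10 mg | 20 mg | 15 mg | 15/10 = 1.5 |
| 20 mg | 40 mg | 25, 30, 35 mg | 35/20 = 1.75 |
| 40 mg | 80 mg | 45, 50, 55, 60, 65, 70, 75 mg | 75/40 = 1.875 |
| 80 mg | none | no reference dose | – |

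If the branch means going below the current dose, the number admitted is zero in every row. These are possible choices, not likely ones. Part 2 doses are not stated, so no count is made there.

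**3. Illustration: AUC0-24 limit reached at 40 mg**

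Assumptions, none given in the documents: log-normal AUC, dose-proportional exposure, and a between-participant CV of 30% (range 20% to 50%). Six new participants receive active drug.

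Method 1 places the highest of the six AUCs at 40 mg exactly at 1,800. The expected maximum of six standard normals is 1.267. With r the ratio of the new dose to 40 mg and σ = √ln(1 + CV²), the chance that at least one of six new participants reaches 1,800 is

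P = 1 − Φ(1.267 − ln r / σ)⁶.

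At CV 30%, σ = √ln(1.09) = 0.294. For 45 mg, r = 1.125 and ln r / σ = 0.401, so P = 1 − Φ(0.866)⁶ = 1 − 0.807⁶ = 0.72.

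Method 2 treats both maxima as random: P(r × new maximum of six ≥ old maximum of six).

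| Next dose | Method 1, CV 20% | CV 30% | CV 50% | Method 2, CV 30% |
|---|---|---|---|---|
| 35 mg | 15% | 23% | 31% | 31% |
| 40 mg (repeat) | 48% | 48% | 48% | 50% |
| 45 mg | 82% | 72% | 63% | 67% |
| 60 mg | >99% | 99% | 92% | 94% |

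At CV 30% under method 1, the smallest step up adds 0.724 − 0.478 ≈ 0.25 to the chance on repeating the dose, and a 1.5-fold step adds 0.991 − 0.478 ≈ 0.51. The ordering is the same at every CV and under both methods.

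**The case against.** The strongest reply is that 7.3 largely settles its own meaning. The drafter used a downward verb for a met criterion and an upward verb, a paragraph later, for the case where escalation is not stopped. To read the required action as allowing an increase, one has to let a verb of descent mean going up. The closing sentence of 7.3 maps naturally to descent if the trigger was on ATH-399A and escalation if it was on placebo. The suspend option in 13.1.5.1 lets escalation resume only when no stopping rule is found to be met. These points stand, and they make a bar the likely intent.

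It also stands that the options in 7.1.1 and 13.1.5.1 are general menus not tied to a trigger, so they do not show that a step up is allowed after one. Escalation needs mutual agreement of the SRC members, and the SRC may stop at any time for undue risk. The start of 7.3 is redacted and the SRC charter was not available; either may say more.

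A reader might infer that the protocol authorises escalation after toxicity, or that the percentages above measure harm. The documents support neither. The first inference runs against the verb and the closing sentence. As to the second, reaching 1,800 again is a second trigger, not a toxicity, and the safety margin behind that limit is not visible.

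The reply does not remove the reference dose. The operative sentence is visible in full in two places and names the wrong level in both. Agreement and discretion are safeguards of judgement, not a dose limit.

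**Conclusion.** The point holds as a wording error in a safety rule, of minor to moderate weight. The required action is bounded by the planned next dose. Taken literally it admits 1, 3 and 7 intermediate doses above the triggering dose after 10, 20 and 40 mg, up to 1.875 times that dose, and it has no reference dose at 80 mg. That count rests only on the planned doses, the capsule strengths and 5 mg steps.

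The likely intent is a bar on stepping up, so the finding is that the text fails to state the bar, not that the sponsor means to escalate. The repeat-breach percentages are illustrative only: they depend on assumed variability, log-normality and dose proportionality, and they concern one criterion. Nothing is claimed about clinical harm, or about Part 2 doses. Confidence is medium because the redacted text and the charter could add a limit.

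**What to change.** In the Synopsis and 7.3, replace the required action with: *Dose escalation stops; any further cohort in that part will receive a dose no higher than the level at which the criterion was met in participants who received ATH-399A.* Keep the phrase that measures against the planned next level only for the case where no criterion is met. Align the options in 13.1.5.1 and, if needed, the SRC charter.

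This leaves the SRC free to repeat the dose or go lower, including after the AUC0-24 limit is reached. Whether to forbid a repeat in that case is a separate policy choice and is not part of this change.

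The cost is one replacement sentence in two places and one alignment, with no change to cohorts, sample size or assessments. The downside is that an intermediate step up after a confirmed trigger would need a protocol amendment. After a trigger at 5 mg, the smallest capsule strength, only a repeat or a stop remains.
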